2.3 STUDY TREATMENT

The study treatment will be delivery of nebulized sodium nitrite by nebulization at the dose of 45 or 90 mg.

Table 1 Dose Limiting Toxicity Criteria

Sign or Symptom	Moderate	Severe ¹
Bronchospasm/ wheezing	Symptomatic but not requiring therapy	Symptomatic and requiring therapy
Decrease in FEV_1	>15%	>25%
SBP ²	Systolic \geq 20 mm Hg drop from pre-dose baseline AND symptomatic, or SBP <80 mm Hg AND symptomatic	Systolic > 30 mm Hg drop from pre- dose baseline AND symptomatic or requiring fluid replacement or other therapy
Dyspnea	Causes more discomfort (than a mild, easily tolerated AE) and interrupts the subject's usual daily activities	Incapacitating and causes considerable interference with the subject's usual daily activities
Cough	Causes more discomfort (than a mild, easily tolerated AE) and interrupts the subject's usual daily activities	Incapacitating and causes considerable interference with the subject's usual daily activities
Hypoxia ³	$SaO_2 > 5\%$ drop from baseline AND symptomatic	$SaO_2 \geq 10\%$ drop from baseline or $SaO_2 < 88\%$ AND symptomatic

Percutaneous methemoglobin ^{4,5}	>5% and <7%	≥7%
Other drug-related signs or symptoms ⁶	Causes more discomfort (than a mild, easily tolerated AE) and interrupts the subject's usual daily activities OR CTCAE v.4 ⁶ Grade 2 toxicity	Incapacitating and causes considerable interference with the subject's usual daily activities OR CTCAE v.4 ⁶ Grade 3 or 4 toxicity

AE = adverse event; CTCAE = Common Toxicity Criteria for Adverse Events; DLT = dose limiting toxicity; SBP = systolic blood pressure; SaO₂ = oxygen saturation (hemoglobin)

1. Severe DLT seen in any subject which is deemed to be study drug-related will preclude further dosing with nebulized sodium nitrite for that subject.
2. Moderate or Severe SBP without symptoms will be continuously monitored with BP measurements every 5 minutes. Symptomatic refers to dizziness or fainting. Discontinuation of further dosing or dose escalation will be based upon follow up blood pressure measurements, subject symptoms and physician-investigator discretion (see Stopping Rules).
3. Moderate or Severe SaO₂ without symptoms will be continuously monitored and recorded every 5 minutes until return of saturation > 92%.

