4. Elevated percutaneous methemoglobin levels measured by pulse co-oximeter will be continuously monitored and confirmed by venous methemoglobin level. Follow up will be based upon the clinical decision of the operating physician and will be documented as such.
5. A single occurrence of venous methemoglobin levels >5% in an individual subject will result in no further dosing for that individual subject for the remainder of the study period.
6. Common Terminology Criteria for Adverse Events v. 4.0 ([CTCAE](#)). CTCAE criteria will be applied if considered related to study drug and confirmed on repeat testing.

2.4 DURATION OF FOLLOW-UP: All subjects will be followed for 14 days +/- a 5 day window after completion of the study treatment. Subjects removed from study for unacceptable adverse events will be followed until resolution or stabilization of the adverse event.

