2.5 SAFETY MONITORING

Prior studies suggested that hypotension and methemoglobinemia may occur with the use of sodium nitrite. The study treatment of inhaled nitrite will be used safely with careful monitoring and prompt discontinuation of the study treatment in response to systemic hypotension with definitions of dose limiting toxicity. The presence of severe DLT deemed to be study-drug related will lead to a discontinuation of the study treatment.

Following study drug treatment, subjects will be evaluated as an outpatient at the clinic on Day 42 (+/- 5 day window). Interval study visits (days 7, 14 and 28) have been included in the study design to ensure subject safety. Subjects will be followed for evidence of acute or delayed adverse effects from the study treatment and to assess their clinical status. All adverse events experienced by subjects will be collected from beginning of visit 1 through final study visit. Study subjects will be routinely questioned about adverse events at study visits. The study investigators will evaluate all subject reported and observed AEs. All untoward medical occurrences observed in subjects receiving the study drug will be recorded on the participants' adverse event worksheets by the study coordinator under the supervision of the principal investigator. AEs occurring pre-treatment, during active treatment and post-treatment will be summarized separately. Subjects continuing to experience toxicity at the off study visit may be

contacted for additional assessments until the toxicity has resolved or is deemed irreversible. If possible, symptoms should be managed symptomatically. In the case of toxicity, appropriate medical treatment should be used.

In addition to these formal evaluations, subjects will be encouraged to immediately contact the study investigator and/or the study coordinator with questions, concerns, or to report new symptoms that occur during their study participation. If appropriate, based upon the evaluation, medical treatments will be provided to subjects, including appropriate referral to physicians or other services at the UPMC.

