2.6 STOPPING RULES

Two distinct scenarios in which subjects must be removed from the study are anticipated.

First, the subject experiences a CF respiratory exacerbation marked by a persistent drop in FEV1 >15% that is not temporally associated with nebulized sodium nitrite administration. The drop in FEV1 would be seen on the first set of spirometry at a visit, prior to dosing of nebulized sodium nitrite for that day. In this case, subjects will be removed from the study and referred to their pulmonologist for treatment of the CF respiratory exacerbation.

Drop in FEV1 >15% on the first set of spirometry, prior to drug administration, on any study visit when compared with baseline spirometry collected at screening.

In the second scenario, nebulized sodium nitrite is associated with a dose-dependent intolerance that will be seen at the dose escalation visit 2, or after receiving the first dose of drug on visit 1. Specific intolerances of concern are acute bronchospasm, hypotension or methemoglobinemia. In this case, if any one of the below occurs at the 45 mg dose, subject will be removed from the study; if any occur at the 90 mg dose, the subject will return to the previously tolerated dose of 45 mg.

Specific criteria for dose-dependent intolerance are:

Decrease in FEV1 by >15% between measurements on an individual study visit.

A decrease in systolic BP > 40 mmHg drop from pre-dose baseline or to <80mmHg and symptomatic.

SaO₂ drop below 88% and symptomatic or SaO₂ desaturation > 5% from baseline and symptomatic

A single occurrence of venous methemoglobin level >5%

Any serious adverse event thought to be possibly related to the study treatment

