2.14.2 WITHDRAWL CRITERIA

Study treatment will be discontinued in individual subjects during the day 0 inhalation if any of the following occurs regardless of symptoms:

- **Decrease in FEV₁ by >15%** between measurements on an individual study visit.
- A decrease in systolic BP > 40 mm Hg drop from pre-dose baseline or to <80mmHg and symptomatic;
- SaO₂ drop below 88% and symptomatic or SaO₂ desaturation > 5% from baseline and symptomatic
- A single occurrence of venous methemoglobin level >5%;
- Any serious adverse event thought to be possibly related to the study treatment

Any serious adverse event thought to be possibly related to the study treatment

If a study subject tolerates the 45 mg dose but develops hypotension, sustained > 15% decrease in FEV₁ (as measured at time points (30min and 120 min), or oxygen desaturation with the 90 mg dose on day 7, the subject will be observed. If after 4 hours of observation the subject's FEV₁ returns to baseline, the subject's SaO₂ is not greater than 5% drop from baseline, and the subject's systolic BP is not greater than 40 mm Hg drop from pre-dose baseline, the subject will be re-challenged with the 45mg dose; if the lower dose is tolerated, the subject will remain in the study at the lower dose.

Subjects will be withdrawn if at any time the investigator feels that it is not in the subject's best interest to continue.

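### After a drug-related severe toxicity at 90 mg, 2.6 and 5.5.2 direct a return to 45 mg while Table 1 footnotes 1 and 5 and 2.5 stop dosing; the Day 7 re-challenge test shares the conflict and omits the symptomatic SBP <80 mmHg limit

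*Combined protocol and SAP*

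**What the plan says.** Two rules end dosing. Footnote 1 to Table 1 (section 2.3) reads "Severe DLT seen in any subject which is deemed to be study drug-related will preclude further dosing with nebulized sodium nitrite for that subject". Section 2.5 agrees: "The presence of severe DLT deemed to be study-drug related will lead to a discontinuation of the study treatment". Table 1 grades as severe, among others, an FEV1 fall >25%, symptomatic SaO2 <88%, and for blood pressure "Systolic > 30 mm Hg drop from pre- dose baseline AND symptomatic" or a need for fluids or other therapy. The moderate blood pressure cell covers a 20 mmHg "drop from pre-dose baseline AND symptomatic, or SBP <80 mm Hg AND symptomatic". Footnote 5 adds a separate stop: "A single occurrence of venous methemoglobin levels >5% in an individual subject will result in no further dosing for that individual subject".

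The stopping rules in 2.6, repeated in 5.5.2, list intolerance events: an FEV1 fall >15% within a visit, an SBP drop >40 mmHg or symptomatic SBP <80 mmHg, symptomatic SaO2 <88% or symptomatic desaturation >5%, venous methemoglobin >5%, and a possibly related serious adverse event. At 45 mg these remove the subject. At 90 mg the instruction is "if any occur at the 90 mg dose, the subject will return to the previously tolerated dose of 45 mg". Section 2.13.1 likewise keeps a subject with a sustained FEV1 fall after 90 mg on 45 mg, with no upper bound on the fall.

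Sections 2.2.1 (visit 2) and 2.14.2 give a same-day re-challenge test. Within or after 4 hours, FEV1 must be back at baseline, SaO2 no more than 5% down, and SBP no more than 40 mmHg down. If so, in the words of 2.14.2, "the subject's systolic BP is not greater than 40 mm Hg drop from pre-dose baseline, the subject will be re-challenged with the 45mg dose".

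**The concern.** Bronchospasm, hypotension and methemoglobinemia are the intolerances the protocol names, and safety is its objective. For several of these events at 90 mg, one part of the protocol orders another dose and another forbids it. Staff must choose on the day of the reaction, and a subject who tolerates the 45 mg re-challenge then doses unsupervised at home.

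The re-challenge test adds to this in two ways. It ignores how severe the event was at its worst. It also keeps the relative SBP limit of the intolerance criteria but drops the absolute one, so a subject who still meets an intolerance criterion can pass.

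**Working it through.** This is a check of rules against each other. The protocol's one computed design figure (N=33, 82% power, one-sided binomial, 0.06 against 0.20) reproduces: rejecting at 5 or more events gives alpha 0.0454 and power 0.8179. The point does not depend on it.

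**Step 1. Step-down against stop, for events at 90 mg.**

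| Event | 2.6 / 5.5.2 | Table 1 footnotes and 2.5 |
|---|---|---|
| FEV1 fall >25% | Listed (>15%, no upper bound): 45 mg | Severe: stop if drug-related |
| Symptomatic SaO2 <88% | Listed: 45 mg | Severe: stop if drug-related |
| Symptomatic SBP drop >40 mmHg | Listed: 45 mg | Severe (>30): stop if drug-related |
| Symptomatic SBP <80 mmHg, drop >30 mmHg | Listed (<80): 45 mg | Severe (>30): stop if drug-related |
| Venous methemoglobin >5% | Listed: 45 mg | Footnote 5: no further dosing |

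The drug-related qualifier does not separate the rules, because 2.6 introduces its list as intolerance associated with the study drug.

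**Step 2. Where the fourth row applies for drops of 31-40 mmHg.** Let P be pre-dose SBP and D the drop. The event is listed when P - D < 80, that is D ≥ P - 79. I assume Day 7 pre-dose SBP is at least the 90 mmHg entry floor.
- P = 90 to 110: every D from 31 to 40 is listed (110 - 31 = 79).
- P = 111 to 119: only some are (115: D = 36-40; 119: D = 40).
- P ≥ 120: none are (120 - 40 = 80).

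**Step 3. Re-challenge after a recovered severe event.** Take a 30% FEV1 fall at 30 and 120 minutes that is back to baseline by 4 hours, with SaO2 and SBP within limits. It passes the test, although footnote 1 and 2.5 stop dosing if it is drug-related. Nothing in the test asks what the worst value was.

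**Step 4. The SBP gap.** Let S be SBP at the check. Three conditions must hold together, with the FEV1 and SaO2 conditions also met:
- an intolerance criterion is still met: S < 80 with symptoms;
- the re-challenge test is passed: P - S ≤ 40;
- the event is not severe, so footnote 1 is silent: P - S ≤ 30 and no therapy given.

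So S runs from P - 30 to 79, which needs P ≤ 109.

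| Pre-dose SBP (mmHg) | SBP at check (mmHg) | Drop (mmHg) |
|---|---|---|
| 90 | 60-79 | 11-30 |
| 95 | 65-79 | 16-30 |
| 100 | 70-79 | 21-30 |
| 105 | 75-79 | 26-30 |
| 109 | 79 | 30 |
| 110 or more | none | - |

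For example, a subject who goes from 100 to 75 mmHg and is still dizzy has a drop of 25 mmHg. Table 1 grades this moderate, 2.6 lists it as intolerance, and the re-challenge test passes it.

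**The case against.** **The rules can be read together.** One could take 2.6 as covering only the non-severe part of its list, with footnote 1 governing the rest. That is sensible, but nothing says so, and it fails for venous methemoglobin >5%: the trigger is the same in 2.6/5.5.2 and footnote 5, so no milder part remains for the step-down. Nor can footnote 1 be confined to the 90 mg dose, since it bars further dosing with the drug.

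**Investigator judgment covers the gap.** This stands in part. Section 2.14 lets the investigator discontinue a subject at any time, and 2.14.2 ends by requiring withdrawal when continuing is not in the subject's interest. Footnote 2 also says "Discontinuation of further dosing or dose escalation will be based upon follow up blood pressure measurements, subject symptoms and physician-investigator discretion", though it opens with SBP changes without symptoms. Treating the subject would, on the natural reading of Table 1, make the event severe and bring in footnote 1. The gap is therefore narrow. Discretion does not say which of two mandatory instructions governs in the main conflict. The request in 2.14 for every effort to retain subjects is general and does not itself direct another dose.

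**Stronger readings that the documents do not support.**
- A reader might infer a separate oxygen gap for baseline SaO2 of 88-92%, where a fall of 5 points or less can end below 88%. With symptoms, SaO2 <88% is already severe and belongs to the conflict. Without symptoms, it meets no listed intolerance criterion.
- A reader might infer that a symptomatic SBP drop of 31-40 mmHg opens re-challenge at any pre-dose SBP. If SBP stays at or above 80 mmHg (say 140 to 105), 2.6 does not list the event. Re-challenge opens only if it counts as not tolerated (2.2.1) or as hypotension (2.14.2), and the protocol defines neither.
- A reader might extend the SBP gap to pre-dose values of 110-119 mmHg. Symptomatic values below 80 mmHg there imply drops above 30 mmHg, which are severe and belong to the conflict.

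**Conclusion.** The main point holds. For the five events in Step 1, the protocol gives opposite dosing instructions and no precedence. The conflict does not need the event to persist; one qualifying event at 90 mg is enough. For all but methemoglobin it needs the event to be judged drug-related. The re-challenge test repeats the problem for severe events that recover.

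The SBP gap is real but secondary. It is limited to pre-dose SBP 90-109 mmHg and needs symptoms and SBP <80 mmHg to last through observation without therapy. It should be rare: section 1.3.3 describes earlier hypotension as immediate (176 mg) or orthostasis as transient (120 mg).

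The documents do not give the share of subjects who would meet either situation at 90 mg in cystic fibrosis, so the ranges show where the rules fail and not how often. No effect on sample size or power is claimed. The SBP ranges assume whole-number readings and a Day 7 pre-dose SBP of at least 90 mmHg.

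**What to change.** In 2.6, 5.5.2, 2.2.1 (visit 2) and 2.14.2, state that Table 1 footnotes 1 and 5 and section 2.5 override both the step-down and the re-challenge to 45 mg. A cross-reference in 2.13.1 would keep it in line. This also settles a drug-related symptomatic drop of 31-40 mmHg without needing a definition of *not tolerated*.

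In 2.2.1 (visit 2) and 2.14.2, allow re-challenge only if no listed intolerance criterion is still present, naming symptomatic SBP <80 mmHg and symptomatic SaO2 <88%.

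The cost is protocol wording and its approval. The limits already exist, and blood pressure, saturation, spirometry and symptoms are already assessed, so no visits or tests are added. The downside is that a few subjects would not be stepped down or re-challenged and would contribute less 45 mg exposure after Day 7.

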2.15 STATISTICAL ANALYSIS

2.15.1 Power Analysis and Sample Size:

The main adverse events reported in CF antibiotic trials are increased cough and change in respiratory symptoms. The overall subject driven discontinuation rate for these symptoms in both the placebo and treatment arms of recent antibiotics studies has ranged from 10-18%, although these symptoms do not necessarily correlate with bronchoconstriction (22, 23). Hypertonic saline is the most osmotically similar agent in use, and it causes 4.5% of children with severe CF lung disease to have an acute drop in FEV₁ of >15% (our stopping threshold) when used for sputum induction(24). Over a 4 week period, recent antibiotic studies have showed a decrease in FEV₁ of 3 to 6.5% in the placebo arms (19, 20, 22), so we are unlikely to have subjects reach the FEV₁ discontinuation threshold if nebulized sodium nitrite is safe but ineffective. Considering these data, we expect a 5-10% rate of discontinuation due to FEV₁ drop >15%, and we would consider up to 20% discontinuation acceptable. At a significance level of 0.05, a sample size of 33 is required to achieve 82% power to detect a difference of 0.14 using a one-sided binomial test, assuming that the population proportion under the null hypothesis is 0.06.

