2.13 ENDPOINTS

2.13.1 Primary endpoint: The primary endpoint is FEV₁ to assess for bronchoconstriction induced by the study compound. We will compare FEV₁ before and at 30, and 120 minutes after dosing on day 0 with 45 mg dose, and day 7 with 90 mg dose. A sustained decrease in FEV₁ > 15% with the 45 mg dose will be considered intolerance and the study subject will be removed from the protocol. If a subject tolerates one week of the 45 mg dose but has a sustained decrease in FEV₁ after getting the first 90 mg dose, the subject will remain on the 45 mg dose for the duration of the study. If a subject experiences a CF respiratory exacerbation as defined by a drop in FEV₁ >15% on the first set of spirometry at any visit compared with baseline spirometry, then the subject will be removed from the study.

2.13.2 Secondary endpoints:

- FE_{NO} (exhaled NO)
- sputum nitrite concentrations
- CF Questionnaire-R subsection
- quantitative bacterial cultures for *P. aeruginosa* and/or *S. aureus*
- methemoglobin levels measured both non invasively and in whole blood
- systolic blood pressure

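### The binomial test in 2.15.1 is powered on discontinuation for an FEV₁ fall, which, read literally, leaves out subjects who react to 90 mg and are stepped down to 45 mg

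*Combined protocol and SAP*

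**What the plan says.** **The tested proportion.** Section 2.15.1 says: "we expect a 5-10% rate of discontinuation due to FEV₁ drop >15%, and we would consider up to 20% discontinuation acceptable". It then gives 33 subjects and 82% power for a one-sided binomial test at 0.05, with a null of 0.06 and a difference of 0.14. One benchmark for the expected rate is that hypertonic saline causes 4.5% of children with severe CF lung disease "to have an acute drop in FEV₁ of >15% (our stopping threshold").

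**The primary endpoint.** Section 2.13.1: "The primary endpoint is FEV₁ to assess for bronchoconstriction induced by the study compound". It continues: "We will compare FEV₁ before and at 30, and 120 minutes after dosing on day 0 with 45 mg dose, and day 7", the day 7 dose being 90 mg. The synopsis calls a sustained fall of more than 15% intolerable without limiting this to one dose.

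**What follows a fall.**
- At 45 mg, sections 2.6 and 2.13.1 remove the subject. Section 2.14.2 says of this dose: "Study treatment will be discontinued in individual subjects during the day 0 inhalation if any of the following occurs regardless of symptoms"; an FEV₁ fall of more than 15% heads the list.
- At 90 mg, section 2.13.1 says that if the subject "has a sustained decrease in FEV₁ after getting the first 90 mg dose, the subject will remain on the 45 mg dose". Sections 2.6 and 5.5.2 likewise return the subject to 45 mg. Section 2.14.2 and the visit 2 text in 2.2.1 add two conditions, recovery by 4 hours and a 45 mg re-challenge: "if the lower dose is tolerated, the subject will remain in the study at the lower dose".

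**Exacerbations.** Section 2.6 also removes subjects with a CF exacerbation "marked by a persistent drop in FEV1 >15% that is not temporally associated with nebulized sodium nitrite administration".

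**The concern.** The trial asks whether inhaled nitrite causes bronchoconstriction, and 90 mg is the dose planned for three of the four treatment weeks. The same physiological event counts as a discontinuation at 45 mg but, on the plain wording, not at 90 mg if the subject continues on 45 mg. Section 2.6 expects intolerance to depend on dose, so the omitted events fall where the plan itself anticipates a reaction.

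The proportion can also include exacerbation removals, which the plan separates in time from dosing. The stated 82% power would then describe retention in the study after an FEV₁ fall, not acute intolerance. The trial could report an acceptable discontinuation rate while a material share of subjects could not take the dose that a later trial would carry forward.

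**Working it through.** **Inputs from 2.15.1:** alpha 0.05 one-sided; p0 = 0.06; p1 = 0.06 + 0.14 = 0.20; n = 33. Section 2.2.1 plans 35 subjects dosed. The plan states no cutoff.

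**1. Reproducing the plan's figure.** For X ~ Binomial(n, p), take the smallest r with P(X ≥ r | p0) ≤ 0.05.
- n = 33: P(X ≥ 4 | 0.06) = 0.134 and P(X ≥ 5 | 0.06) = 0.045, so r = 5.
- Power = P(X ≥ 5 | 0.20) = 0.818, which matches the stated 82%.

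The arithmetic is right. The issue is what is counted.

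**2. Who is counted, read literally.**

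| Event | Outcome in the documents | A discontinuation? |
|---|---|---|
| Fall >15% at 45 mg, day 0 | Removed (2.6, 2.13.1, 2.14.2) | Yes |
| Fall >15% at 90 mg, recovered by 4 h, 45 mg tolerated | Stays on 45 mg (2.14.2, visit 2) | No |
| Fall >15% at 90 mg, not recovered by 4 h | Back to 45 mg under 2.6; not addressed in 2.14.2 or visit 2 | Unsettled |
| Drug-related fall >25% at 90 mg | No further dosing (Table 1, note 1); back to 45 mg (2.6) | Conflicting |
| First-spirometry fall >15% from screening | Removed as exacerbation (2.6) | Yes, not separated |

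**3. Illustration of size.** The documents do not give the share f of acute falls that end in step-down, so f is assumed. Take true acute intolerance of 20% and count no exacerbation removals. The counted rate is 0.20 × (1 − f), and power is P(X ≥ 5) at n = 33:
- f = 0.10: rate 0.18, power 73%
- f = 0.25: rate 0.15, power 56%
- f = 0.50: rate 0.10, power 23%

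Counting exacerbation removals pushes the other way. With f = 0.25 and an assumed independent 5% exacerbation rate, the counted rate is 1 − 0.85 × 0.95 = 0.1925 and the test rejects with probability 79%. Those extra counts are not drug effects, so they do not repair the measure, but they show that the direction and size of the net error are not fixed by the documents.

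**4. Cutoff for the number dosed.** At n = 35, P(X ≥ 5 | 0.06) = 0.056, above 0.05. The cutoff becomes 6 or more: alpha 0.017, power 73%.

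**The case against.** **Discontinuation is undefined.** Section 2.15.1 labels the 15% fall a stopping threshold and speaks of subjects reaching a discontinuation threshold. Table 1, note 2 (on blood pressure) even mentions discontinuing dose escalation. On that looser reading, crossing the threshold is the event, 90 mg reactors are counted, and the flaw is only loose wording. This stands as a reason for less certainty. It does not remove the point: no section adopts that reading, and 2.14.2 uses discontinuation for day 0 but says that the 90 mg reactor remains in the study.

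**The events are still reported.** A reader might infer that 90 mg falls disappear from the results. They do not. Section 2.13.1 compares FEV₁ before and after both doses, section 5.5.6.3 makes a test finding that changes dosing an adverse event, and 2.15.2 tabulates adverse events. But that comparison has no stated test, null or limit. It is equally true that no section makes the binomial test a formal decision rule; it is simply the only test named.

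**The power loss is assumed.** A reader might infer that power collapses, since a half share gives 23%. The documents do not support any particular share, and the illustration sets exacerbation removals to zero. Nor did the plan set 20% as a limit for acute intolerance; it set it for discontinuation. This objection stands in full against any claimed figure.

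**Conclusion.** The concern holds in a limited form. On the literal reading, which the step-down rules favour, the powered proportion leaves out subjects who react to the first 90 mg dose and continue on 45 mg. It also mixes in exacerbation removals.

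A reader might go further and say that every 90 mg reactor is missed, or that those who fail to recover are counted. Neither follows. Table 1, note 1 stops dosing after a drug-related severe toxicity, in conflict with 2.6, and no section settles the outcome of a subject not recovered at 4 hours.

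The drop from 82% to 56% is an illustration under stated assumptions (20% true acute intolerance, a quarter of events ending in step-down, no exacerbation removals counted), not an estimate. The firm conclusion is that the stated 82% applies to acute intolerance only if step-downs are counted and exacerbation removals are not, and the text does not say so. This should be fixed.

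**What to change.** In 2.13.1 and 2.15.1:
- Define the tested event once per subject: an FEV₁ fall of more than 15% from the same visit's pre-dose value, after dosing on day 0 or day 7, that is sustained at 30 and 120 minutes or leads to removal or step-down to 45 mg. Count it whether or not the subject stays in the study. The count then no longer depends on how the conflict between Table 1 and 2.6 is resolved.
- Use all subjects dosed on day 0 as the denominator.
- Report exacerbation removals separately, and the 45 mg and 90 mg rates each with an exact confidence interval.
- Confirm that 6% and 20% apply to this either-dose event.
- State the cutoff for the number dosed: 33, 5 or more (alpha 0.045, power 82%); 35, 6 or more (alpha 0.017, power 73%).

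**Cost.** The pre-dose, 30 and 120 minute spirometry is already scheduled on both days, so no new measurement is needed. The headline rate may look less favourable. Stated power is 73% if all 35 are dosed. The 6% null may need fresh justification for two exposures: if each dose carried 4.5% independently (an assumption that borrows the saline figure), the either-dose rate would be 1 − 0.955² = 8.8%, and 5 or more of 33 would have a false-positive rate of 0.16. In that case the cutoff, and possibly the sample size, would have to be reworked.
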